20. Tumor imaging: to be performed at screening, within 28 days from treatment start (in case a tumor imaging is already available in the specified time window, it has not to be repeated); at the end of even months (even cycles) of treatment and at EoT. The EoT assessment is to be performed only if it was not performed in the previous 4 weeks. In patients withdrawn for reasons other than progressive disease (PD), during follow up, tumor assessment should be performed every 2 months, until PD or until a new antitumor therapy starts. On treatment, a time window of -2/+5 days is allowed. Patients with responding tumors (complete or partial response) must have response confirmed by CT scan at least 4 weeks after the 1 st documentation of response. The same method of assessment and technique should be used to characterize and follow the same lesion at screening, during treatment and at EoT. Ct scan is the desirable method for lesion measurement (see Section 11.3.1).
21. BCLC and TNM Staging: TNM and BCLC staging will be requested at enrollment for all patients, including collection of clinical related additional info
22. Survival follow up: post-treatment survival status, including additional information (e.g. new anticancer therapy), will be collected at the 28-days follow up visit and thereafter every 2 months from last treatment administration until death. Telephone contacts are acceptable for these assessments.
23. Biomarkers sampling: peripheral blood samples will be collected at Enrollment (≤ 7 days before Cycle1 Day1) for analysis of selected molecular alterations in circulating free DNA (cfDNA) from plasma
24. PK blood sample: during the Phase II, a sparse sampling procedure will be adopted; blood sampling for PK is to be performed at cycles 1, 2, 3 and 4 (refer to Table 5 for details).
25. End of Treatment (EoT): visit to be performed within 7 days from the decision of discontinuing the study drug.
26. Off treatment assessments: 28 days, and no more than 35 days, after discontinuation of study treatment patients will return for the following assessments: ECOG PS, blood pressure and heart rate, hematology, blood chemistry, coagulation, concomitant medications, adverse events and survival follow up. Further follow up contacts will be scheduled every 2 months from last treatment administration, until death, to assess the survival status, including possible additional information.

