28 day follow up for laboratory abnormalities: in case hematology, blood chemistry, coagulation, study drug-related and clinically significant abnormalities persist beyond the 28-days follow up assessment, they should be followed until they resolve or the Investigator assess them as chronic or stable, or until alternative anticancer therapy is initiated. In this case, the reporting period will end at the time the new treatment is started.
28 days follow up for adverse events: the AEs reporting period ends 28 days after the last study treatment administration. The following events should be followed after the end of the reporting period: serious adverse events (SAEs) with outcome "not recovered" or "unknown" and study drug-related AEs with outcome "not recovered" or "unknown". They have to be followed until they resolve or the Investigator assess them as chronic or stable, or until alternative anticancer therapy is initiated. In this case, the reporting period will end at the time the new treatment is started.
* Cycle 1 Day 1 assessments: evaluations do not need to be repeated before study drug administration if they were performed at screening within 24 hours from treatment start.
• only even cycles

Table 5. Investigational Assessments details for Phase II

	Cycle 1 (Days)								Cycles 2 and 4 (Days)						Cycle 3 (Days)					
	D1			D8		D15			D22	D1	D15			D26 - 28		D15				
Timing related to EoI (hour)	0.0 [§]	15min – 2h	>2h – 6h	Pre	0.0 [§]	Pre	0.0 [§]	15min – 2h	>2h – 6h	Any	Pre	Pre	0.0 [§]	15min – 2h	>2h – 6h	Any	Pre	0.0 [§]	15min – 2h	>2h – 6h
PK blood sample ^c	X	X ^{Od}	X ^{Ev}	X ^{Od}	X ^{Ev}	X	X	X ^{Ev}	X ^{Od}	X	X	X	X	X ^{Od}	X ^{Ev}	X	X	X ^{Ev}	X ^{Od}	

c. **PK blood samples:** all patients enrolled in the Phase II portion of the study will undergo blood draws for PK analysis (central laboratory) based on their enrollment number (odd or even), as detailed below.

Odd patients (X^{Od})

Cycle 1:

Day 1: 5 minutes before the end of infusion (0.0§), from 15 minutes to 2h after the end of study drug administration

Day 8: before the start of infusion (pre-dose)

Day 15: before the start of infusion (pre-dose), 5 minutes before the end of infusion (0.0§), from >2h to 6h after the end of study drug administration

Day 22: one sample, at any time

Cycles 2 and 4:

Day 1: before the start of infusion (pre-dose)

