9.2.3.2. Re-treatment Criteria and Cycle Delay

A new cycle of treatment may begin when hematological and non-hematological toxicities are Grade ≤ 1 or have recovered to baseline values.

If these conditions are not met, treatment should be delayed for 1 week to allow for recovery. If, after 1-week delay, re-treatment criteria are met, then the new cycle can be initiated with a starting dose defined based on the toxicities observed in the previous cycle as outlined in the [Table 6](#).

If, after this period, toxicities do not recover to the pre-defined level, the patient will be withdrawn from the treatment, unless the Investigator believes treatment continuation is in the patient best interest. In this case, a maximum delay of 2 weeks (up to day 42 from cycle start) will be allowed.

Table 6. Dose Reductions/Treatment Discontinuations for NMS-01940153E Based on the Worst Grade (as per NCI CTCAE Criteria, Version 5.0) Observed During a Treatment Cycle and in the Prior Treatment Cycle

Toxicity	Dose Adjustment during treatment cycle	Next cycle Starting Dose
Hematological Toxicities		
Neutropenia Grade 3	Omit dose; when resolved to \leq Grade 1 within the same cycle, decrease one dose level.	Start at or maintain the decreased dose level.
Neutropenia Grade 4	Omit dose; when resolved to \leq Grade 1 within the same cycle, decrease one dose level.	Start at or maintain the decreased dose level.
Febrile Neutropenia	Omit dose; when resolved, decrease one dose level.	Start at or maintain the decreased dose level.
Thrombocytopenia Grade 3 associated with bleeding or thrombocytopenia Grade 4	Omit dose; when resolved to \leq Grade 2 within the same cycle, decrease one dose level.	Start at or maintain the decreased dose level.
Anemia Grade 3	Omit dose; when resolved to \leq Grade 2 within the same cycle, decrease one dose level.	Start at or maintain the decreased dose level.
Anemia Grade 4	Study treatment discontinuation.	Study treatment discontinuation.
Other Grade 3 Hematologic Toxicities	Omit dose; when resolved to \leq Grade 2 within the same cycle, decrease one dose level.	Start at or maintain the decreased dose level.
Other Grade 4 Hematologic Toxicities	Study treatment discontinuation.	Study treatment discontinuation.
Nausea and/or Vomiting		
Grade \geq 3 despite optimal management of the event §‡	Omit dose; when resolved to \leq Grade 2 within the same cycle, decrease one dose level.	Start at or maintain the decreased dose level.
Diarrhea		

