11.3.1. Tumor Imaging

Baseline tumor imaging (by CT scan, PET or MRI) has to be performed at screening within 28 days prior to the treatment start. On treatment, tumor assessments will be performed every even month (i.e., end of Cycle 2, 4, 6 etc) or whenever a clinical deterioration is observed and at the end of last cycle, unless a tumor assessment was performed within the previous 4 weeks. In patients withdrawn for causes other than disease progression, during follow up, regular tumor imaging assessments will be performed every 2 months, until PD or until a new antitumor therapy starts. On treatment, a time window of -2/+5 days is allowed.

Patients with responding tumors (complete or partial response) must have response confirmed at least 4 weeks after the first documentation of response.

CT scan is the desirable method for lesion measurement. MRI is acceptable provided that the size of the measurable lesion is twice the slice thickness of the MRI. MRI should be performed at pre-treatment in case of known or suspected CNS involvement.

According to RECIST, the same method and technique (CT scan or MRI) should be used to characterize each identified and reported lesion at baseline and during the following assessments.

Imaging-based evaluation should be preferred to clinical examination when both could be used to assess the antitumor effect of the treatment.

According to mRECIST, tumor assessment should be performed with the administration of intravenous contrast to obtain a dual-phase imaging of the liver. To prevent possibly allergic reactions to intravenous Contrast Medium (CM), patients with previous reaction(s) to CM, asthma even drug controlled and/or food or drug allergies will be treated with a premedication (corticosteroid).

Patients can be followed with either contrast-enhanced spiral CT (preferably with use of multi-slice scanners) or contrast-enhanced dynamic MRI. Each modality has advantages and disadvantages, and mRECIST does not recommend one modality over another.

However, it is recommended that the same imaging modality be used throughout the study. Ultrasound – including contrast-enhanced ultrasound – is not recommended for the general use of mRECIST.

PET/CT is not accepted for treatment assessment in guidelines.

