Evaluable Set (ES): this is the patient population for the primary efficacy analysis. This set will include patients of the TS who have measurable disease at baseline assessed according to RECIST 1.1 and at least one tumor evaluation on treatment, unless they die before the first tumor on-treatment assessment (i.e. if the patients died within 61 days from the start of the treatment considering that the first on treatment tumor assessment is foreseen at the end of cycle 2 with a time window of -2/+5 days), in which case they will be considered treatment failure. Moreover, subjects must have disease relapsed or refractory to the standard of care treatment including an immunocheckpoint inhibitor as first line and at least a tyrosine kinase inhibitor, not exceeding 3 lines of prior systemic treatment. Patients who received the RP2D defined in phase I portion as starting dose and from cycle 2 a dose increment of 25% (as per protocol version 4.0 dated 30-Jun-2022) were considered not evaluable for efficacy analysis (intra-patient dose escalation no more applicable as per protocol version 5.0). In detail, the evaluable population for primary efficacy endpoint will consist of a subset of the evaluable population up to the total number of subjects pre-determined by the interim for futility and final analyses. This means that, if the number of evaluable subjects exceeds the planned total number of subjects at either stage, the exceeding subjects will not be considered for primary efficacy analysis. Subjects will be counted into the primary evaluable population, consecutively, based on the date of first NMS-01940153E administration.

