9.7.2. Secondary Efficacy Endpoint(s)

For the Phase I part, the objective tumor response (Partial and Complete response) will be reported in patients' data listings.

Statistical Analysis Plan

ORR will be also calculated for Phase II part only, as the percentage of evaluable patients with best response equal to complete response (CR) or partial response (PR) as defined by investigator-assessed mRECIST. Binomial exact 95% confidence intervals will be also provided.

Time-to-event endpoints (i.e. DoR, PFS and OS): they will be carried out on treated set for Phase I and evaluable set for Phase II, respectively. The individual calculated times will be presented in patients' data listings together with the identification of censored vs. failure status. Time-to-event endpoints will be also summarized using Kaplan Meier (KM) curves and further characterized in terms of median, 6-month, 9-month and 12-month estimates with the corresponding 95% confidence intervals, for Phase II part only.

Reverse Kaplan-Meier method [9] will be used to estimate length of follow-up for DoR, PFS and OS by reversing censored and event observations, if applicable.

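### On-treatment scans follow the cycle count, so permitted cycle delays move the scan dates and make recorded PFS depend partly on toxicity delays

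*Protocol*

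**What the plan says.** - Protocol Section 7, Table 4 footnote 20 sets Phase II on-treatment imaging "at the end of even months (even cycles) of treatment and at EoT". It adds: "On treatment, a time window of -2/+5 days is allowed".
- The Table 4 symbol for the on-treatment scan reads "only even cycles".
- Protocol 11.3.1 spells the timing out as "every even month (i.e., end of Cycle 2, 4, 6 etc) or whenever a clinical deterioration is observed".
- SAP Section 7 reads it the same way: "the first on treatment tumor assessment is foreseen at the end of cycle 2 with a time window of -2/+5 days". It uses that timing to define an early death that counts as treatment failure: "if the patients died within 61 days from the start of the treatment".
- Protocol 9.2.3.2 delays a new cycle by one week if toxicity has not recovered. At the investigator's discretion, "a maximum delay of 2 weeks (up to day 42 from cycle start) will be allowed". Protocol Section 10 applies the limit to any cycle.
- After withdrawal for reasons other than progression, footnote 20 and Section 11.3.1 move imaging to every 2 calendar months.
- SAP 9.7.2 has the Phase II time-to-event endpoints "further characterized in terms of median, 6-month, 9-month and 12-month estimates".

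Neither document says that a scan keeps its calendar date when a cycle starts late.

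**The concern.** A cycle lasts 28 days only when the next one starts on time. When it does not, every later scan moves back, and the displacement accumulates. Radiographic progression is dated at the scan that shows it, so a delayed patient is on average recorded as progressing later with no change in the disease. The delay is driven by toxicity, so assessment timing becomes related to tolerability. Protocol 5.3 names dose-related neutropenia as the main safety feature, so some delays should be expected.

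There is no comparative arm, so no between-arm contrast cancels the effect. It enters the absolute PFS estimates and any comparison with outside data, and it could enter the exploratory work relating baseline factors to outcome.

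A second consequence reaches the primary endpoint. The SAP's early-death cut-off is built on the undelayed calendar, so it can disagree with the date on which a delayed patient was actually due a scan.

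**Working it through.** **The plan's own figure.** The SAP's 61 days is two cycles plus the late window: 2 × 28 + 5 = 61. It reproduces exactly, with zero delay.

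**Scan calendar.** Scan k falls at the end of cycle 2k, taken as that cycle's day 28. The 2k − 1 earlier between-cycle delays have then accrued. With delay d in every cycle, scan day = 56k + (2k − 1)d.

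- d = 0: days 56, 112, 168, 224
- d = 7: days 63, 133, 203, 273
- d = 14: days 70, 154, 238, 322

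The interval between scans grows from 56 to 70 or 84 days. The latest in-window first scan moves from day 61 to 63 + 5 = 68 or 70 + 5 = 75.

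**PFS model (assumption).** True PFS is exponential with median 3.1 months, the regorafenib figure in Protocol 3.1; the documents give no PFS assumption for this drug. In days, 3.1 × 30.44 = 94.4, so S(t) = 2^(−t/94.4). Progression is dated at the next scan, with no deaths and no scans triggered by deterioration.

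- Observed median = first scan with S ≤ 0.5.
- Landmark PFS = S at the last scan on or before the landmark (days 183, 274, 365).
- Mean lag = Σ(t_k − t_(k−1))·S(t_(k−1)) − 94.4/ln 2, with t_0 = 0.

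| Delay in every cycle | Observed median (days) | Mean lag (days) | 6-month PFS | 9-month PFS | 12-month PFS |
|---|---|---|---|---|---|
| 0 | 112 | 29.9 | S(168) = 29.1% | S(224) = 19.3% | S(336) = 8.5% |
| 7 days | 133 | 36.5 | S(133) = 37.6% | S(273) = 13.5% | S(343) = 8.0% |
| 14 days | 154 | 43.0 | S(154) = 32.3% | S(238) = 17.4% | S(322) = 9.4% |
| True value | 94.4 | – | 26.1% | 13.4% | 6.8% |

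**Less extreme delay.** Simulation with a 7-day delay in 30% of cycles gives a median of 119 days and a mean lag of 32.0 days, about 2 days more than with no delay.

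**Deaths.** If 30% of events are exactly dated deaths, the mean lags are 21.0, 25.6 and 30.1 days for 0, 7 and 14 days in every cycle. The delay then adds 4.6 or 9.1 days.

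**A different true median.** At 6.0 months the observed median is 224, 203 and 238 days. It falls in the middle case because a median can land only on scan dates.

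**Duration of response.** Simulation with a true median of 6 months and onset within 56 days gives mean observed minus true duration, among detected responders, of +1.9, +2.4 and +3.2 days for 0, 7 and 14 days. Mean observed duration rises (293, 301, 308 days) mainly because fewer short responses are detected (90.1%, 87.7%, 85.5%).

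**Early-death rule.** Suppose Cycle 2 starts 14 days late and the patient dies unscanned on day 70. There is no on-treatment assessment, and the death falls after day 61. Under the SAP's parenthesis the patient is in neither branch of the Evaluable Set. Under Protocol 12.2, which sets no day limit, the same patient is a treatment failure. The exposed interval runs from day 62 to the first scan, at the latest day 68 or 75.

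**The case against.** The strongest reply is that a delay in every cycle for every patient is extreme. Doses missed within a cycle are skipped and do not lengthen it. Toxicity leads to dose reduction and eventually withdrawal, and withdrawal without progression returns the patient to calendar imaging. Scans at clinical deterioration and at end of treatment catch some progressions earlier, and deaths are dated exactly. PFS and duration of response are secondary and descriptive, with no decision rule attached. The event-date and censoring rules sit in a separate appendix that is not available here. All of this stands. It limits the size and makes the tabulated shifts upper-end values. It does not keep scans on the calendar, and deterioration scans miss asymptomatic radiographic progression.

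A reader might infer three stronger things that the documents and arithmetic do not support.

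- That all planned PFS summaries are inflated by delay. Mean observed PFS lengthens, but 9-month PFS falls from 19.3% to 13.5% with 7-day delays, and some medians fall.
- That duration of response is lengthened in the same way. Onset is also detected later, so the two lags nearly cancel within a patient.
- That a delay in every cycle stretches the whole calendar to 10 or 12 weeks from the start. Only one between-cycle delay precedes the first scan, so it falls on day 63 or 70 if the end of a cycle means day 28, as the SAP's 61 days implies. If it means the day before the next cycle begins, the first scan could be as late as about day 84; the documents do not define it.

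**Conclusion.** The point holds as a modest design weakness that is cheap to remove. On-treatment imaging is tied to even cycles, cycles may start late, and recorded PFS therefore depends partly on toxicity delays. Under the stated model, delays in every cycle add about 7 days (7-day delay) or 13 days (14-day delay) to the mean detection lag and move the observed median by 21 or 42 days. Much of that movement in the median is the step from one scan date to the next. At 7 days in 30% of cycles the mean effect is about 2 days. The real delay frequency is not in the documents, so no single figure can be assigned to this trial. The landmarks are better described as unstable than as biased upward.

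The 61-day rule is the part that bears on the primary endpoint. It can remove an early death from the ORR denominator when Cycle 2 starts late, where the protocol's own definition would count a failure. Few patients are likely to fall in so short an interval, but the rule should not depend on dosing delay.

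**What to change.** In Table 4 footnote 20 and Protocol 11.3.1, replace the even-month and even-cycle timing with imaging every 8 weeks (−2/+5 days) counted from Cycle 1 Day 1, irrespective of cycle delays or omitted doses. Keep the same calendar after treatment stops without progression, until progression or new antitumor therapy. Change the Table 4 symbol for the imaging row to match. In SAP Section 7, refer to the 8-week scan instead of the end of Cycle 2; the 61-day cut-off (56 + 5) then agrees with the scan schedule as it stands.

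This is a wording change that touches no dose or treatment rule. The intended 8-week interval is unchanged. The costs are that some scans will not coincide with a cycle-end visit, and that delayed patients keep the 8-weekly frequency instead of having fewer scans. The ordinary lag of about 30 days from 8-weekly imaging under the model remains; only the delay-driven part goes.

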8. ENROLLMENT PROCEDURES

Patients considered suitable will be informed about study and procedures, both verbally and by written information. Patients will be given all the time they need for reading information provided, discuss and question them and ask others' opinion. Patients who will decide to participate in the study will sign and date the informed consent form (ICF) before starting any trial related procedures; concomitantly, the Investigator will also sign and date the form.

After the signature of the ICF, a screening number will be centrally assigned to the patient, allowing the screening process for eligibility to begin. All screening evaluations must be completed and reviewed to confirm that potential suitable patients meet all eligibility criteria. Upon completion of the screening evaluation, patients meeting all the eligibility criteria will be enrolled and, for Phase I patients, dose level assigned; the enrollment number will be centrally assigned and maintained throughout all the study duration. Patients who do not meet all the eligibility criteria will be declared screening failure.

Screening and enrollment numbers assignment and, for Phase I patients only, also dose level, will be centrally managed by the Sponsor within one working day. The investigator will maintain a screening and enrollment log to record details of all participants screened and to confirm eligibility or record reasons for screening failure, as applicable.

No study drug will be dispensed to a patient until the entire registration/enrollment process is completed. It is recommended to start the treatment within 1-4 days from patient enrollment.

For the phase I portion of the study, the Sponsor will notify all the participant sites of the inclusion of a new patient and will inform them of the next possible enrollment date. The enrollment will be competitive among the participating sites.

8.1. Screening Procedures

Following the obtaining of the ICF, in order to get the patient's screening number, the Investigator will enter the information required in a web application made available to centers by the Sponsor (details are reported in the Study Manual).

The screening number will be sequential for the center where the patient has been recruited. The screening number assignment is automatically notified by e-mail.

In case the web application is not available because of any reason, the Investigator will enter the information required in a paper registration/enrollment form and fax/email it to the Sponsor (details are reported in the Study Manual).

8.2. Enrollment procedures

Upon completion of the screening evaluation, the Investigator will enter the information in the web application, confirming patient's eligibility or declaring the patient as screening failure; patients meeting all the eligibility criteria will be enrolled. The enrollment number will be assigned centrally and automatically notified by e-mail (details are reported in the Study Manual).

The enrollment number will be sequential regardless of the center where the patient has been recruited.

In case the web application is not available because of any reason, the Investigator will enter the information required in a paper registration/enrollment form and fax/email it to the Sponsor (details are reported in the Study Manual).

The eligibility of a patient is an Investigator's responsibility. Verification of the confirmed eligibility will be performed by the Sponsor or authorized personnel delegated by the Sponsor during the study.

